8.0 STATISTICAL CONSIDERATIONS

8.1 General Design Issues

This is a Phase I multi-center, open label, non-comparative study to assess the safety and pharmacokinetics of raltegravir administered to full-term neonates, aged ≤ 48 hours (protocol Version 1.0) and ≤ 60 hours (protocol Version 2.), at risk of acquiring HIV-1 infection. The goal is to determine a dose of raltegravir, that is safe, well-tolerated and meets PK targets, administered as an oral granules suspension to neonates and infants in the first 6 weeks of life. Both the mother and the infant will be enrolled, with the mother having only a study entry visit and the infant followed through 24 weeks of life.

Safety data will include signs/symptoms, diagnoses and laboratory test results, which will include results of evaluations specified in the protocol and results from the infant's clinical care. Infants will be evaluable for safety analysis if they received at least one dose of raltegravir. For CRF reporting and analysis of safety data, the sites' assessments of AE relationship to raltegravir will be used. However, with regards to participant safety and PK evaluations which will support the selection of a dose for a given cohort, the protocol team will also have input as to the causality and drug relation of specific adverse experiences. Regular monitoring of RAL safety, which could result in dose or study modification, described in detail in Section 8.5.

Approximately 50 infants and their mothers will be enrolled in order to have a minimum of 12 and 20 PK evaluable participants in Cohorts 1 and 2, respectively. If a participant has unevaluable PK data, which reflects uncertainty about appropriate exposure to the study medication then the participant will be excluded from PK analyses and will be replaced.

The study design consists of two cohorts with the following dosing regimens of raltegravir in addition to standard PMTCT:

Cohort 1:

Raltegravir as oral granules for suspension, per Section 5.11 administered as a single dose within 48 hours of birth, with a second dose administered at 7-10 days of life

Cohort 2:

Raltegravir as oral granules for suspension, per Section 5.11 administered as daily dosing through 6 weeks of life with first dose given within 48 hours of birth for RAL-naïve infants and between 12 and 60 hours of birth for RAL-exposed infants.

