8.2 Outcome Measures

(Outcome Measures are for infants only; maternal data are to be used as covariates, not as outcomes)

8.21 Primary Endpoints for Cohorts 1 and 2

Toxicity Endpoints: Toxicity from study entry through 6 weeks of life

- Adverse events of Grade 3 or 4 severity or death (primary safety endpoint for final analysis)
- Suspected adverse drug reaction (SADR) of Grade 3 or 4 severity or death (primary safety endpoint for dose finding guidelines described in Section 8.52) but secondary safety endpoint for the analyses described in Section 8.71)

Pharmacokinetic Endpoints: (See Section 9.0: Clinical Pharmacology Plan)

8.22 Primary Response Variables for Cohorts 1 and 2 Pharmacokinetic parameters (See Section 9.0)

8.23 Secondary toxicity endpoints for Cohorts 1 and 2: Toxicity from study entry weeks through 24 weeks of age

- Adverse events of Grade 3 or 4 severity or death
- Suspected adverse drug reaction (SADR) of Grade 3 or 4 severity or death

8.24 Secondary Response Variables for Cohorts 1 and 2

- UGT1A1 genotype (presence or absence of *28/*28 genetic variant)
- SLCO1B3 (rs2117032-C/T) genotype
- Hyperbilirubinemia defined as total bilirubin exceeding 16.0 mg/dL or infant receiving phototherapy, or transfusion therapy, or other therapies for hyperbilirubinemia

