January 3, 2017	V3.0	
 • Specified that two final analysis reports will be generated: 
 ○ For protocol Version 1.0: A report focusing on Cohort 1 (both RAL naïve and exposed groups) and Cohort 2 RAL naïve group ○ In the event that protocol Version 2.0 is approved: A report focusing on Cohort 2 (both RAL naïve and exposed groups) • Added the definition of wide analysis visit windows • Added summary tables: 
 ○ Study treatment status ○ Age at 1st RAL dose for Cohort 2 infants ○ Summary of worst grade baseline events • Added a section on Cohort 2 adherence to RAL • Modified the summary tables for summarizing infant infection status • Clarified that Adverse Events (AEs) and Suspected Adverse Drug Reactions (SADRs) exclude events assessed by the team as “baseline” or “ongoing baseline” • Clarified the definition of primary and secondary safety endpoints • Added infant listings which will be used internally at SDAC in writing the SDAC final analysis report and will be provided to the manuscript writing team • Removed analysis for CL/F among SLCO1B3 genotypes. • Added the definition of wild-type vs. mutation for UGT1A1 and SLCO1B3 genotypes • Added mock-up tables for CL/F analysis between different genotypes of UGT1A1 • Added mock-up tables for Hyperbilirubinemia analysis among different genotypes of UGT1A1 and SLCO1B3 • Updated team roster
-----------------	------	---

Table of Contents

1	Purpose of the Analysis Plan	5
2	Protocol Overview	5
3	Protocol Team Roster	7
4	Outline of Planned Analysis	8
4.1	Screening and Entry	8
4.1.1	Accrual	9
4.1.2	Eligibility Violations and Analysis Exclusions	9
4.2	Baseline Characteristics	9
4.3	Participant and Study Status	11
4.4	Data Completeness for Safety Data	12
4.5	RAL Adherence for Cohort 2 Infants	13
4.6	Safety Analysis for SDAC Final Reports	14
4.7	Safety Analysis for Dose Finding and Possible Early Study Discontinuation	15
4.8	Infant Infection Testing.....	17
4.9	Genotype Analysis	17

Table of Tables

Table 1: Eligibility Violation and Analysis Exclusion Example	9
Table 2: Cohort 1 Infant Baseline Characteristics (mock-up table)	10
Table 3: Number of Cohort 1 Infants Accrued and Evaluable for PK/Safety Analysis (mock-up table)	11
Table 4: Infant Safety Data Collection Schedule for Cohort 1	12
Table 5: Infant Safety Data Collection Schedule for Cohort 2	13

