This is a Phase I multi-center, open label, non-comparative study to evaluate the safety and pharmacokinetics (PK) of raltegravir (RAL) administered to HIV-1-exposed full-term (≥ 37 weeks of gestation) neonates at high risk of acquiring HIV-1 infection. The goal is to determine the appropriate dosing regimen of RAL oral granules for suspension that can be safely administered to neonates and infants in the first 6 weeks of life.

This study will enroll approximately 50 neonates in order to accrue a minimum of 32 PK evaluable high risk HIV-1-exposed neonates and their mothers across Cohort 1 and Cohort 2. Mother-infant (M-I) pairs will enroll at the time of delivery up to 48 hours of life, which is the latest time for administration of first neonatal RAL dose. Cohort 1 opened first and accrual to Cohort 2 was contingent upon neonates enrolled in Cohort 1 successfully meeting safety criteria and providing adequate PK data so that the dosing regimen was developed for daily dosing through 6 weeks of age for Cohort 2. Through Protocol Version 1.0 LoA #2 Cohort 2 RAL-naïve group was opened to accrual with the following dosage: 1.5 mg/kg once daily during Days 1-7 of life, 3.0 mg/kg twice daily during Days 8-28 of life, and 6.0 mg/kg twice daily during Days 29-42 of life.

At the time of this SAP update, Cohort 1 (both RAL-naïve and RAL-exposed groups) is closed to accrual and follow-up and Cohort 2 RAL-naïve group is closed to accrual but follow-up is ongoing. The final accrual numbers are 10 M-I pairs for Cohort 1 RAL-naïve, 6 M-I pairs for Cohort 1 RAL-exposed, and 26 M-I pairs for Cohort 2 RAL-naïve groups under protocol Version 1.0. The team estimated that the study will take 3 years to fully accrue under protocol

Version 1.0. Protocol Version 2.0 is currently being drafted and if approved, will open accrual to Cohort 2 RAL exposed group.

PK evaluable infants are those whose PK results provide data on the primary PK parameters of interest. If a participant has unevaluable PK data, which reflects uncertainty about appropriate exposure to the study medication, the participant will be excluded from PK analyses and will be replaced. PK analyses will be done by the protocol pharmacologist.

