4.6 Safety Analysis for SDAC Final Reports

Purpose:

To list the endpoints and tables of primary and secondary safety analyses for the SDAC final reports.

Analysis Program Validation:

Code review required. Primary analysis for primary safety endpoints will require double coding.

Data:

Infant safety data are adverse clinical and laboratory events reported on the following CRFs: Hematology and Liver Chemistries (LBW0093), Signs/Symptoms (PE6831), Diagnosis (PE6852) and Death (PE1414). (The following variables in the SDAC SAS datasets will be used: EVENTDSC, EVNGRDE, FORMNM and FORMTYP in EVENTS table; and TBILCV, BILPHOTO, BILTRANS, BILOTH and BILOTHSP in LBW0093).

Analysis:

There will be two final SDAC reports. The first report will focus on Cohort 1 (both RAL-naïve and exposed groups) and Cohort 2 RAL-naïve group. The second report will include Cohort 2 (both RAL-naïve and exposed groups). The safety analyses will include all infants who have had at least one dose of RAL. For Cohort 2, if there was dose adjustment after the interim analysis, a sensitivity analysis will be performed on infants who were enrolled after dose adjustment and only took the adjusted dose. Adverse Events (AEs) and Suspected Adverse Drug Reactions (SADRs) will exclude events classified by the team as “baseline” or “ongoing baseline” events.

- Safety endpoints for Cohorts 1 and 2 in SDAC final reports
 - Primary safety endpoint for the final analysis:
 - Adverse events of Grade 3 or 4 severity in the EVENTS table or death reported in the Death CRF with onset date at or after study entry through 6 weeks (i.e. through 49 days of age) of life
 - Secondary safety endpoints for the final analysis:
 - Adverse events of Grade 3 or 4 severity in the EVENTS table or death reported in the Death CRF with onset date at or after study entry through 24 weeks of life (through 196 days of age)
 - Suspected adverse drug reaction (SADR*) of Grade 3 or 4 severity or death with onset date at or after study entry through 6 weeks (through 49 days of age) of life
 - Suspected adverse drug reaction (SADR*) of Grade 3 or 4 severity or death with onset date at or after study entry through 24 weeks of life (i.e. through 196 days of age)

* For the SDAC final report, SADRs will include the following attribution to drug: 11 – “Definitely related”; 12 – “Probably related”; and 13 – “Possibly related”.

- Summary tables for Cohorts 1 and 2 in the SDAC final reports (Analysis for primary and

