4.7 Safety Analysis for Dose Finding and Possible Early Study Discontinuation

Purpose:

To list the endpoints and summary tables of safety analysis for dose finding and possible early study discontinuation. Reports will be generated at full accrual to cohort 1 and at interim and full accrual to cohort 2.

Analysis Program Validation:

Code review required. Primary analysis will require double coding.

Data:

Infant Safety Data are adverse clinical and laboratory events reported in Hematology and Liver Chemistries ((LBW0093), Signs/Symptoms (PE6831), Diagnosis (PE6852) and Death (PE1414) CRFs. (The following variables in the SDAC SAS datasets will be used: EVENTDSC, EVNGRDE, FORMNM and FORMTYP in EVENTS table; TRACKCD and RELATSP in TRAC table; and RAL1ST, RAL1RS, RAL2ST, RAL2RS in TXW0276 CRF).

Analysis:

Infants who have been excluded from the PK analyses, due to evidence of problematic exposure to the study medication, will be excluded from evaluation of the safety guidelines. AEs and SADRs will exclude events classified by the team as “baseline” or “ongoing baseline” events.

- a) Safety endpoints for Cohorts 1 and 2 in dose finding and possible early study discontinuation
 - Safety endpoints
 - based on data through 6 weeks (i.e. through 49 days) of life:
 - i. Life threatening event or death judged to be a SADR or Grade 4 event that is judged to be probably or definitely attributable to the study medication
 - ii. Treatment discontinuation due to non-life threatening Grade 3 or 4 severity SADR, judged to be at least possibly treatment related

Notes: During the regular monitoring, the team will assess whether an AE is life threatening and the assessment will be entered in the TRAC table. Treatment discontinuation due to an AE will be on the TXW0276 CRF.

- b) Summary table for the interim and cohort full accrual safety reports (analysis for dose finding and possible early study discontinuation).
Note: Only the overall summary will be provided since we are expecting very few infants meeting the safety endpoint.

Table: Summary table showing number (%) of the proportion of infants who meet the safety endpoints for dose finding and possible early study discontinuation.

Table 7: Summary of Infants Meeting the Safety Endpoints for Dose Finding and Possible Early Study Discontinuation

Endpoint	Number and Proportion

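### SAP 4.6 drops events the team labels baseline or ongoing baseline from the primary safety endpoint, which protocol 8.21 does not provide for, and no rule keeps a post-entry rise to Grade 3 or 4 in the count

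*SAP*

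**What the plan says.** Protocol 8.21 sets the window as "Toxicity Endpoints: Toxicity from study entry through 6 weeks of life" and names as the first endpoint "Adverse events of Grade 3 or 4 severity or death (primary safety endpoint for final analysis"). Protocol 8.71 estimates the proportion of infants who meet it, with an exact 90% interval, in all infants given at least one dose. Neither section removes baseline events.

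SAP 4.6 keeps that endpoint and adds an onset condition: "with onset date at or after study entry through 6 weeks (i.e. through 49 days of age) of life". In the same section it adds a second filter: "Adverse Events (AEs) and Suspected Adverse Drug Reactions (SADRs) will exclude events classified by the team as" baseline or ongoing baseline. SAP 4.7, on dose finding, repeats the filter: "AEs and SADRs will exclude events classified by the team as" those two labels. The version history lists it under V3.0 (January 2017): "Clarified that Adverse Events (AEs) and Suspected Adverse Drug Reactions (SADRs) exclude events assessed by the team as" baseline or ongoing baseline. SAP section 2 says that at this update Cohort 1 "is closed to accrual and follow-up and Cohort 2 RAL-naïve group is closed to accrual but follow-up is ongoing". Protocol 8.1 describes the design: "This is a Phase I multi-center, open label, non-comparative study".

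Neither document defines the two labels, says when they are assigned, says how a change in grade is handled, or plans an analysis without the exclusion. SAP 4.6 does plan a worst-grade table of baseline events, per-infant listings for the writing team, and a separate bilirubin table.

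**The concern.** The protocol endpoint is all-cause: a qualifying grade inside the window is enough. The SAP makes it depend on a label that the team assigns while it knows the treatment and follows the infant's course. Under protocol 8.1, safety analyses use the sites' assessments of relatedness, and the team's input on causality is tied to dose selection. A team decision on which events enter the final primary proportion is therefore an addition.

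At stake is whether the main safety estimate reports what 8.21 promised. An infant with a mild abnormality before entry that becomes severe on raltegravir is a case a first neonatal dosing study needs to count. Nothing in the text requires that it be counted, and in groups this small one infant moves the estimate visibly.

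**Working it through.** **Step 1. Which records can the exclusion affect?** The table combines protocol 8.21 with the SAP 4.6 onset condition and filter.

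| Record | Protocol 8.21 | SAP 4.6 |
|---|---|---|
| Onset before entry, no later record | Outside the window | Already out by the onset condition |
| Same abnormality, unchanged grade, recorded again after entry | Not addressed | Can be labelled ongoing baseline |
| Grade 3/4 onset after entry, before first dose | Counts | Can be labelled baseline |
| Lower grade before entry, Grade 3/4 after entry | Counts if the rise is an event | Can be labelled ongoing baseline |
| First appears after the first dose | Counts | Filter not relevant |

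The first row needs no filter. The filter therefore matters only for the middle three rows. The second is a sensible use of it. The third and fourth can remove events that fall within 8.21. The filter can lower the proportion or leave it unchanged; it cannot raise it.

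**Step 2. The plan's own figure.** The documents give no figure for the effect of the exclusion. The only stated precision for this endpoint is protocol Table 14, labelled 90% Clopper-Pearson. The limits are the beta quantiles

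L = Beta(0.05; x, n−x+1), U = Beta(0.95; x+1, n−x).

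For 0/8 this gives U = 1 − 0.05^(1/8) = 0.31; Table 14 prints 0.37. For 2/8 it gives (0.05, 0.60); Table 14 prints (0.03, 0.65). All ten printed rows agree with 95% limits to within 0.01. That is a separate matter, but the intervals below are true 90% limits and will not match Table 14.

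**Step 3. Effect per infant.** Inputs: 26, 10 and 6 pairs accrued (SAP section 2: Cohort 2 RAL-naïve, Cohort 1 RAL-naïve, Cohort 1 RAL-exposed), and a minimum of 8 for Cohort 2 RAL-exposed (protocol 8.4). I assume that all were dosed. An infant whose only qualifying event is excluded stays in the denominator and leaves the numerator, so the proportion falls by 1/n:

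- n=26: 1/26 = 3.8 points
- n=10: 1/10 = 10 points
- n=8: 1/8 = 12.5 points
- n=6: 1/6 = 16.7 points

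The number of such infants is not given. As an assumed range, take 0 to 2 per group with no other infant having an event. The entries show the result if those infants are counted (90% interval); excluding them returns the first column.

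| n | 0 counted | 1 counted | 2 counted |
|---|---|---|---|
| 26 | 0% (0–11%) | 3.8% (0–17%) | 7.7% (1–22%) |
| 10 | 0% (0–26%) | 10% (1–39%) | 20% (4–51%) |
| 8 | 0% (0–31%) | 12.5% (1–47%) | 25% (5–60%) |
| 6 | 0% (0–39%) | 16.7% (1–58%) | 33.3% (6–73%) |

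The fall of 1/n per infant is the same at any starting count.

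**The case against.** - **Ordinary treatment-emergent practice.** Excluding pre-existing conditions is usual, and the team may well record a rise in grade as a new event. SAP section 1 refers to a Study Monitoring Plan for the details of monitoring; it is not among the documents, and a grade rule may be there. This stands as a limit: leaving out worsening is permitted by the text, not stated. But the usual practice counts worsening from baseline, and the SAP, which defines the endpoint, does not say so.
- **Legitimate uses.** Repeat records of an unchanged abnormality should not count. This stands, and the fix keeps that use.
- **Excluded events remain visible.** The baseline table and listings allow an exclusion to be traced. They do not put the infant back into the primary proportion.
- **Bilirubin.** Because newborn bilirubin is often raised and is measured before enrollment, a reader might infer that bilirubin toxicity could be hidden. The documents do not support this. SAP 4.6 gives a separate proportion with exact 90% interval for infants with total bilirubin above 16.0 mg/dL or treated for hyperbilirubinemia, built from laboratory-form fields and, as described, not dependent on the label. Protocol 4.41 also excludes infants above phototherapy thresholds at entry.
- **Dose finding.** A reader might infer that SAP 4.7 contradicts the protocol in the same way. It largely does not: protocol 8.52 to 8.523 already limit the life-threatening, fatal and Grade 4 criteria to new events, and the other criterion also requires treatment discontinuation. What remains is that neither document says whether a rise in grade makes an event new.
- **No comparator.** With no control arm, the label cannot favour one arm, and the Study Monitoring Committee generally reviews the same types of report as the team. This rules out a between-arm bias, but not a lower single-group estimate.

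**Conclusion.** The point holds for the primary endpoint in SAP 4.6. The SAP applies an undefined, team-assigned exclusion that protocol 8.21 and 8.71 do not contain, and it can act only on records dated after entry. A worsening to Grade 3 or 4 may be lost from the primary proportion, at a cost of 3.8 points per infant at n=26 and 12.5 points at n=8, if all accrued infants were dosed and the infant has no other qualifying event.

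Two further readings go beyond the text. One is that events have been removed in numbers that change the conclusion; the documents give no count, and the 0 to 2 range above is an assumption. The other is that the rule was added late to lower the observed rate. Cohort 1 was complete at the V3.0 update, but the history calls the change a clarification, and practice before it may have been the same. The timing is a reason to prefer a fixed rule to discretion; it is not evidence of motive.

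**What to change.** In SAP 4.6, replace the team classification with a rule. Exclude an event only if it was present before study entry and its grade never rises above the pre-entry grade. Count any later increase to Grade 3 or 4 as a new event with onset on the date of the increase. If there is no pre-entry abnormality on record, nothing is excluded. The anchor should be study entry, as in protocol 8.21; anchoring at first dose would drop events between entry and dosing that 8.21 counts.

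Report the 8.21 endpoint with no baseline exclusion next to it, for each group. In SAP 4.7, use the same grade-increase rule to say what is a new event under protocol 8.52 to 8.523. Keep the baseline table and listings.

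The cost is SAP wording, a short derivation and one extra row per table. Grade and onset date are already part of the SAP 4.6 endpoint definitions, but the EVENTS variables listed there include no date, so the date field should be named. The downside is that the reported rate may be somewhat higher, because natural progression of neonatal abnormalities is counted.

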4.7 Safety Analysis for Dose Finding and Possible Early Study Discontinuation

Purpose:

To list the endpoints and summary tables of safety analysis for dose finding and possible early study discontinuation. Reports will be generated at full accrual to cohort 1 and at interim and full accrual to cohort 2.

Analysis Program Validation:

Code review required. Primary analysis will require double coding.

Data:

Infant Safety Data are adverse clinical and laboratory events reported in Hematology and Liver Chemistries ((LBW0093), Signs/Symptoms (PE6831), Diagnosis (PE6852) and Death (PE1414) CRFs. (The following variables in the SDAC SAS datasets will be used: EVENTDSC, EVNGRDE, FORMNM and FORMTYP in EVENTS table; TRACKCD and RELATSP in TRAC table; and RAL1ST, RAL1RS, RAL2ST, RAL2RS in TXW0276 CRF).

Analysis:

Infants who have been excluded from the PK analyses, due to evidence of problematic exposure to the study medication, will be excluded from evaluation of the safety guidelines. AEs and SADRs will exclude events classified by the team as “baseline” or “ongoing baseline” events.

- a) Safety endpoints for Cohorts 1 and 2 in dose finding and possible early study discontinuation
 - Safety endpoints
 - based on data through 6 weeks (i.e. through 49 days) of life:
 - i. Life threatening event or death judged to be a SADR or Grade 4 event that is judged to be probably or definitely attributable to the study medication
 - ii. Treatment discontinuation due to non-life threatening Grade 3 or 4 severity SADR, judged to be at least possibly treatment related

Notes: During the regular monitoring, the team will assess whether an AE is life threatening and the assessment will be entered in the TRAC table. Treatment discontinuation due to an AE will be on the TXW0276 CRF.

- b) Summary table for the interim and cohort full accrual safety reports (analysis for dose finding and possible early study discontinuation).
Note: Only the overall summary will be provided since we are expecting very few infants meeting the safety endpoint.

Table: Summary table showing number (%) of the proportion of infants who meet the safety endpoints for dose finding and possible early study discontinuation.

Table 7: Summary of Infants Meeting the Safety Endpoints for Dose Finding and Possible Early Study Discontinuation

Endpoint	Number and Proportion
Life threatening adverse event or death judged to be a SADR or Grade 4 event that is judged to be probably or definitely attributable to the study medication	
Treatment discontinuation due to non-life threatening Grade 3 or 4 severity SADR, judged to be at least possibly treatment related	
Meeting any of the two safety guideline endpoints	

